15.4 Personal information of the study subjects

The sponsor or the designee shall affirm the principle of the protection of study subjects' private/personal information. Throughout this study, study subject ID codes shall be used to link the subject's source data to the sponsor's study database and study-related documents. Limited information on study subjects such as gender, age, and date of birth may be used within the scope of all applicable laws and regulations for identification of study subjects and confirmation of accuracy of study subject ID code.

For verification of the conduct of the study in compliance with this protocol and the Ethical Guidelines for Medical and Health Research Involving Human Subjects, the sponsor shall require the principal investigator to provide the study sponsor's designee, representatives of regulatory authorities, designated auditors, and committees such as the Ethical Review Board direct access to study subjects' original medical records (source data or documents), including laboratory test results, admission and discharge records during a subject's study participation, and autopsy reports. The principal investigator or investigator shall obtain specific authorization of the study subject as part of the informed consent process for access to study subject's original medical records by study sponsor's designee and representatives of regulatory authorities (see Section 15.3).

When providing a copy of source documents to the sponsor, the principal investigator or investigator shall delete information that may lead to identification of an individual (name and address of study subject, other personal information not recorded on the CRF of the study subject).

15.5 Consultation windows for the study subjects or persons related to the study concerned

The principal investigator shall establish a contact service to respond to inquiries concerning this clinical study from study subjects or concerned people. Details of the contacts for inquiries will be described in the informed consent form and information sheet.

15.6 Financial burden or reward to the study subjects

Of the expenses for this clinical study, the sponsor shall offer compensation for medical treatment not covered by health insurance as study expenses. The study subjects shall pay expenses for medical treatment covered by ordinary health insurance.

In addition, the principal investigator shall pay expenses such as transportation expenses for participation in this clinical study to the study subjects at each visit from the research funds. Details of the financial burden on the study subjects and rewards shall be described in the informed consent form and information sheet.

15.7 Benefits and inconveniences to the study subjects

15.7.1 Benefits to study subjects

By participating in this clinical study, the study subjects may understand one's own condition of vascular endothelial function in detail.

15.7.2 Inconveniences to study subjects

By participating in this clinical study the burden of the study subject may increase as number of visits will increase compared to daily medical care.

15.8 Attribution of study results and access rights

15.8.1 Attribution of study results

The study results and data obtained from this study shall belong to the sponsor.

15.8.2 Data access rights

Access rights for all data and information generated from this study will be given to personnel approved by the sponsor. In addition, secondary use (meta-analysis, etc.) of the data obtained in this clinical study may be possible if used in such a way that the data shall not be linked to personal identification information.

15.9 Reporting of results, publication, disclosure, and clinical study registration policy

15.9.1 Reporting of results, publication and disclosure

The principal investigator shall report a written summary of results of the study to the chief executive of the study site and provide the sponsor with all the results and data obtained from the study. Only the sponsor may disclose the study information to other principal investigators, investigators or regulatory authorities during the study period, except when required by laws and regulations. The sponsor shall be responsible for publication of the study protocol and study-related results (including the public web site) except for other cases permitted in the study contract.

During the study period and after the end of study, the sponsor or the designee should promptly summarize the results and present it to medical journals and academic conferences, etc. The sponsor may publish any data or information obtained from the study (including data and information provided by the principal investigator) without obtaining agreement of the principal investigator.

The principal investigator or the investigator should obtain the prior written approval from the sponsor when publishing the information obtained in this study at an academic conference, etc.

15.9.2 Clinical study registration

To ensure that information on clinical study is made accessible to the public in a timely manner and to comply with applicable laws, regulations, and guidelines, Takeda Pharmaceutical Company Limited shall register all clinical study being conducted in patients around the world at public trial registration sites, including at least the website(s) of ClinicalTrials.gov (and) Japan Pharmaceutical Information Center Clinical Trials Information (JAPIC), before initiation of the clinical study. On such websites, the study location (city, country), study subject recruitment status, and contact information for Takeda Pharmaceutical Company Limited are open to the public.

15.9.3 Clinical trial results disclosure

Takeda Pharmaceutical Company Limited shall post the study results, irrespective of the nature of the results, at the public trial registration site(s) of ClinicalTrials.gov (and) JAPIC in accordance with applicable laws and regulations.

15.10 Insurance and compensation for injury

In case of injuries, each study subject in the clinical study must be insured in accordance with the regulations applicable to the study site where the subject is participating. The sponsor or the designee shall buy an insurance policy to compensate for health injury in study subjects.

Healthy injury in a study subject will be compensated as specified in the study contract.

Compensation-related questions by the principal investigator or investigators should be made to the sponsor or the designee.

Appendix A Schedule for Study Procedures

Visit timing	Week	Screening period	Treatment period			Discontinuation ^(e)
	Day	-4	0	4	8	
Window (day)		-29 to -1	-15 to -1	14 to 41	42 to 70	Within 3 days after the last dose
Visit No.		1	2	3	4	
Informed consent		X				
Inclusion/exclusion criteria		X				
Demographic data, medical history, previous treatment drug(s)		X				
Physical examination		X	X	X	X	X
Height		X				
Body weight		X				
BMI		X				
Vital signs		X	X	X	X	X
Concomitant drugs ^(a)		X	X	X	X	X
Concurrent disease		X	X			
Laboratory tests						
Hematology/ Serum chemistry		X ^(c)	X	X	X	X
Specific lipoprotein fraction assay ^(b)		X ^(c)	X	X	X	X
Lipoprotein assay ^(b)		X ^(c)	X	X	X	X
Mean particle diameter of LDL/HDL ^(b)		X ^(c)	X	X	X	X
Fatty acid fraction in total lipids		X ^(c)	X	X	X	X
Others		X ^(c)	X	X	X	X
Study drug prescription			X	X		
Treatment compliance				X	X	X
Food and drink consumption before the visit			X	X	X	X
Evaluation of adverse events			←X→	←X→	←X	←X

(a) All concomitant drugs will be recorded.

(b) By HPLC

(c) To be performed before the Visit 2 tests

(d) Medication will be started the day after the completion of all the tests of Week 0. The start date of medication will be referred to as Day 1.

(e) To be performed to the extent possible

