2.0 STUDY SUMMARY

Sponsor: Takeda Pharmaceutical Company Limited	Study drug: Omega-3-acid ethyl esters
Study title: Exploratory study of the effects of omega-3-acid ethyl esters on the lipid and lipoprotein profile in the blood	
Protocol number: TAK-085-4002	

Clinical study design:
 
To explore the effects of omega-3-acid ethyl esters on the lipid and lipoprotein profile in the blood in hyperlipidemic patients receiving a hydroxymethylglutaryl-coenzyme A (HMG-CoA) reductase inhibitor in comparison with the control group of patients not treated with omega-3-acid ethyl esters in an unblinded manner by use of high performance liquid chromatography (HPLC) using highly-sensitive gel filtration columns, which is a technique for analyzing lipoprotein.
 
Study subjects who gave consent and were assessed as eligible in the eligibility assessment will be stratified by the factors of “fasting triacylglycerol (TG; < 300 mg/dL or ≥ 300 mg/dL) and age (< 65 years or ≥ 65 years) at the start of the screening period” and allocated to either the group treated with omega-3-acid ethyl esters or the group not treated with omega-3-acid ethyl esters (1:1 ratio).
	

Objectives:
 
To explore the effects of 8-week treatment with omega-3-acid ethyl esters on the lipid and lipoprotein profile in the blood in hyperlipidemic patients receiving a HMG-CoA reductase inhibitor by use of HPLC in comparison with the control group of patients not treated with omega-3-acid ethyl esters.
	
Subjects: Hyperlipidemic patients receiving a HMG-CoA reductase inhibitor	

Planned number of study subjects:
 
50 patients evaluable for the primary endpoint (25 patients in the group treated with omega-3-acid ethyl esters, 25 patients in the group not treated with omega-3-acid ethyl esters)
	
Number of study sites:
 
Around 5 sites

Dose and method of administration:
 
Omega-3-acid ethyl esters 2 g is orally administered immediately after meal twice daily.
	
Route of administration:
 
Oral

Duration of treatment:
 
8 weeks
	
Duration of evaluation:
 
Screening period: 4 weeks

	Treatment period: 8 weeks Total: 12 weeks

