9.3.1 Screening period (Visit 1)

At Visit 1 (Day -29 to Day -1 before the start of study drug administration), the study shall be explained using the informed consent form to the study subjects who meet the inclusion criteria (except for 3) in Section 7.1 and do not meet any of the exclusion criteria in Section 7.2, and consent shall be obtained in accordance with Section 15.3.

Tests, observations, and evaluations to be performed at Visit 1 (Day -29 to Day -1 before the start of study drug administration) are shown below.

- Informed consent
- Demographic data, medical history, previous treatment drug(s)
- Physical examination
- Height, body weight and BMI
- Vital signs
- Concomitant drugs
- Concurrent disease
- Laboratory tests (fasting)

Items to be checked: Food and drink consumption before visit

- Confirm that alcohol was not consumed from 9:00 pm 2 days before the visit and food was not consumed from 9:00 pm the day before the visit

- Confirm that excessive eating/drinking and extreme change in dietary content were not made on the day before the visit.

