13.3 Determination of the number of planned study subject

50 patients evaluable for the primary endpoint

(25 patients in the group treated with omega-3-acid ethyl esters, 25 patients in the group not treated with omega-3-acid ethyl esters)

[Rationale for the number of planned study subjects]

The number of planned study subjects is based on the feasibility to explore the effects of omega-3-acid ethyl esters on the lipid and lipoprotein profile in the blood. The number of planned study subjects is same in the group treated with omega-3-acid ethyl esters and the group not treated with omega-3-acid ethyl esters, which is not based on a statistical consideration.

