2 TIME WINDOW

For each assessment, observation and evaluation item, evaluable data is selected according to the following table. When there are multiple data exist within a time window, the one with the closest date to the reference date is adopted, and if the differences from the reference date are the same for multiple data, the later one is adopted.

< Vital Sign, Laboratory Tests, Lipoprotein Fraction >

Time Point	Reference Date	Time Allowance
		Number of Study Days
Week 0	-1	-15~-1
Week 4	28	14~41
Week 8	56	42~70

*Treated with Omega-3 FAE: The day before study drug administration is indicated as “Day -1” and “Day 1” for the administration day.

Not Treated with Omega-3 FAE: The day of visit at Week 0 is indicated as “Day -1” and “Day 1” for the next day after the visit.

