3 ANALYSIS SET

- Full Analysis Set
The subjects who were randomized and given at least one dose of the study drug.
- Safety Analysis Set
The subjects who are given at least one dose of the study drug.

4 CONSIDERATIONS for ANALYSIS

- Significance level, Confidence coefficient
Significance level of 5%(2-sided) will be used for analysis.
Confidence coefficient of 95% (2-sided) will be used for all confidence intervals.
- Display digit
[Mean, Confidence coefficient, Quartiles]
Round to the one digits lower than significant digits of the data.

[Standard Deviation]

Round to the 2 digits lower than significant digits of the data.

[Minimum and Maximum Values]

Display the data at the significant digits.

[Proportion, Percentage]

Round to the one decimal place.

[P-value]

Round down to four decimal places. If p-value is less than 0.0001, display “p<0.0001”

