7 EFFICACY EVALUATIONS

7.1 Primary Endpoint and the Analytical Methods

Analysis Set: Full Analysis Set

Analysis Variables: Change of sd LDL-C by Lipoprotein fraction and particle size of LDL

Time Point : Week 0, Week 4, Week 8

Stratified Variable: Fasting Triglycerides (Week -4)

[Min<= - <300, 300<= - <Max]

Age (Week -4) [Min<= - <65, 65<= - <Max]

Analysis Methods:

- (1) Summary statistics of observed value and 95% confidence interval for the mean will be calculated by treatment groups and time point. In addition, Mean (+/-SD) plots will be made by treatment group and time point. Mean differences and the 95% confidence interval (two-sided) will also be provided.
- (2) The same analyses described in (1) will be performed on percent change from baseline.
- (3) Subgroup analysis of observed value and percent change from baseline will be conducted by stratified variables described above. Summary statistics, 95% confidence interval for the mean, mean differences and the 95% confidence interval (two-sided) will be provided.
- (4) The same analyses described in (3) will be performed on percent change from baseline.

- (5) ANCOVA (analysis of covariance), with Fasting Triglycerides at week -4 (Min ≤ - <300, 300 ≤ - <Max), and Age at week -4 (Min ≤ - <65, 65 ≤ - <Max) as covariate, Treatment group as independent variable, will be applied to the data of percent change at Week 0 to Week 8. (alpha=0.05 through an ANCOVA strategy)

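### No planned efficacy analysis uses the Visit 1 lipoprotein and fatty-acid values, and the Week 8 ANCOVA adjusts for no measured pre-treatment value of the outcome

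*Protocol*

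**What the plan says.** Protocol Appendix A marks the lipoprotein fraction assay, the lipoprotein assay, the LDL/HDL mean particle diameter and the fatty-acid fraction at Visit 1 and again at Visit 2. Footnote (c), attached to the Visit 1 entries, reads "To be performed before the Visit 2 tests". Protocol 9.3.1 also lists fasting laboratory tests among the Visit 1 procedures. Under Protocol 9.3.2 a subject is notified to the Registration Center only after the Visit 2 tests are complete, so both samples come before allocation.

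SAP section 2 sets the windows for the group headed "< Vital Sign, Laboratory Tests, Lipoprotein Fraction >". It has rows for Weeks 0, 4 and 8 and none for Week -4, and it takes one value per window, the one nearest the reference date. SAP 7.1 gives "Time Point : Week 0, Week 4, Week 8", and SAP 7.2 and 7.3 use the same time points. Protocol 13.1.3.1 itself takes percentage change from Visit 2.

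The ANCOVA in SAP 7.1(5), carried into 7.2, models percent change from Week 0 to Week 8 on treatment, Week -4 fasting TG class and Week -4 age class. In the baseline table of SAP 6.2.1, TG and age appear at Week -4 and Week 0, but the HPLC variables at Week 0 only.

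Protocol 13.3 plans "50 patients evaluable for the primary endpoint", 25 per arm, a number "which is not based on a statistical consideration". SAP section 4 states: "Significance level of 5%(2-sided) will be used for analysis".

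**The concern.** A single Week 0 reading carries its full day-to-day and assay variation into every percent change. The planned ANCOVA removes none of it, because no measured pre-treatment value of the outcome is in the model. A second pre-treatment reading of each variable is scheduled for every subject and enters no efficacy comparison, and the documents give no reason.

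Such values are fixed before allocation, so using them as covariates cannot bias the randomised comparison. With 25 per arm and a sample size set on feasibility, the width of the between-arm interval largely decides what the trial can say. Using assays already in the schedule costs far less than recruiting more patients.

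**Working it through.** **Inputs from the documents.** 25 per arm (Protocol 13.3); two-sided 5% (SAP section 4); Visit 1 on Day -29 to -1 and Visit 2 on Day -15 to -1 (Appendix A); ANCOVA terms as in SAP 7.1(5). No effect size, SD, power or between-visit correlation is stated, so there is no planned figure to reproduce. All correlations below are assumptions.

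**Step 1. Scale.** In SD units of the analysed variable (normal approximation), the 95% interval half-width for the difference is 1.960 × √(2/25) = 0.55. The difference detectable with 80% power is (1.960 + 0.842) × √(2/25) = 0.79.

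**Step 2. Equal correlation r between all visits.** Treat percent change as a change score, set the variance at each visit to 1, and let the TG and age classes explain nothing. The residual variances are:

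- planned (change from Week 0, no baseline covariate): 2(1 − r)
- Week 0 added: 1 − r²
- Week 0 and Visit 1 added: 1 − 2r²/(1 + r)

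| r | planned | + Week 0 | + both | cut, Week 0 alone | cut, both | extra cut from Visit 1 |
|---|---|---|---|---|---|---|
| 0.5 | 1.000 | 0.750 | 0.667 | 25% | 33% | 11% |
| 0.6 | 0.800 | 0.640 | 0.550 | 20% | 31% | 14% |
| 0.7 | 0.600 | 0.510 | 0.424 | 15% | 29% | 17% |
| 0.8 | 0.400 | 0.360 | 0.289 | 10% | 28% | 20% |

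The first two cuts are against the planned model. The last column is against a model already holding Week 0.

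**Step 3. Unequal correlations.** Let a be the correlation of Visit 2 with Week 8, b that of Visit 1 with Week 8, and c that of Visit 1 with Visit 2. The variance explained by both is (a² + b² − 2abc)/(1 − c²).

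| a | c | extra cut if b = a | extra cut if b = a − 0.05 |
|---|---|---|---|
| 0.6 | 0.75 | 8.0% | 3.6% |
| 0.7 | 0.85 | 7.8% | 2.1% |
| 0.8 | 0.90 | 9.4% | 1.3% |

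First row, last column: (0.36 + 0.3025 − 0.495)/0.4375 = 0.383. The residual is 0.617 against 0.640, a cut of 3.6%. If correlation decays multiplicatively with time, b = ac, the explained variance returns to a², and Visit 1 adds nothing.

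**Step 4. Cost of the extra parameter.** Intercept, treatment, two classes and Week 0 leave 50 − 5 = 45 residual degrees of freedom. One more covariate costs about 1/45, roughly 2%. The net contribution of Visit 1 beyond Week 0 therefore runs from about −2% to about 18%.

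**Step 5. Check by simulation.** The planned percent-change ANCOVA was simulated at 25 per arm with no treatment effect, selection on Visit 1 TG of 150 to <400 mg/dL, r of 0.6 to 0.9 and assumed CVs of 2% and 30%. Relative to the planned model, the variance of the treatment estimate was 0.81 to 0.97 with Week 0 added and 0.73 to 0.80 with both added. These ratios already include the cost of the extra parameters and extend to r = 0.9, so the 20% to 27% reduction is a little below the Step 2 figures.

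**The case against.** The strongest reply is that nothing is wrong. A single last pre-dose baseline is conventional and is fixed by Protocol 13.1.3.1; the trial is exploratory, has no power target and is largely descriptive. That stands, and it is why this is an efficiency point.

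The size can also be challenged. Nominally Visit 1 lies 12 weeks before Week 8 and Visit 2 lies 8 weeks before, so Visit 1 may well predict less. Protocol 7.3.1 prohibits other lipid-lowering agents from Visit 1, while exclusion 5 bars only those started in the preceding 4 weeks, so some Visit 1 samples might reflect an agent that is absent at Visit 2. Neither point biases a pre-allocation covariate, but both weaken the equal-correlation model. The lower end of the range must therefore be zero, or slightly negative after the extra parameter. Much of the gain against the planned model comes from Week 0 alone.

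A reader might infer that the screening visit adds no precision, or that the SAP discards its data. The documents do not support either. Week -4 TG and age classes are stratification factors and ANCOVA covariates. They gave no gain in the simulation (variance ratio without them 0.97 to 0.98), but could help if response depends on TG. For serum TG itself, a secondary variable, the TG class is a coarse pre-treatment value. Because SAP section 2 selects by study day, a Visit 1 sample on Day -15 to -1 would become the Week 0 value if the Visit 2 value were missing. The listings in SAP section 9 are not restricted by visit.

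A reader might also want the mean of the two visits as the reference for percent change, since its change-score variance is 1.5(1 − r) against 2(1 − r), as if 25 per arm were about 33. That departs from Protocol 13.1.3.1, and because eligibility depends on Visit 1 TG it can bring regression to the mean into within-arm changes.

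**Conclusion.** The point holds as an efficiency improvement. The Visit 1 lipoprotein and fatty-acid values are scheduled before allocation and enter no planned efficacy analysis, and the Week 8 ANCOVA adjusts for no measured pre-treatment value of the outcome beyond the TG class.

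Against the planned ANCOVA, Week 0 and Visit 1 together would cut residual variance by roughly 28% to 33% if all visits correlate equally at 0.5 to 0.8. The share due to Visit 1, once Week 0 is in the model, is between about 0% (correlation decaying with time) and about 20% (equal correlation of 0.8), before the cost of roughly 2%. The interval between Visits 1 and 2 is not fixed, which adds to the uncertainty. No stated figure is wrong, and the planned comparison is not biased on this account.

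**What to change.** Amend the SAP as follows.

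- Keep Visit 2 (Week 0) as the reference for percent change.
- In the Week 8 ANCOVA of 7.1(5) and 7.2, add the Week 0 value of the analysed variable and its Visit 1 value as covariates. The alternative is the mean of the available pre-treatment values, used as a single covariate only. Choose one before the data are seen.
- Add a Visit 1 record to section 2, identified by visit number, so that a sample on Day -15 to -1 is not counted in both windows.
- State how a missing Visit 1 value is handled, consistently with the no-imputation rule in SAP 10.2. Copying Week 0 into the Visit 1 covariate would be a substitution. The mean of the available values avoids this, since it reduces to Week 0.

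The mean has a price: it weights both visits equally. Its explained variance is (a + b)²/(2(1 + c)). With a = 0.8, b = 0.75 and c = 0.90 this is 2.4025/3.8 = 0.632, leaving 0.368 against 0.360 for Week 0 alone, about 2% worse. Two separate covariates let the data set the weights at the cost of one degree of freedom.

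The change needs SAP wording and programming only; the assays are already scheduled. If the sponsor prefers to leave Visit 1 out, the SAP should say why these values are collected and not analysed, and still consider the Week 0 covariate.
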